### **Informed Consent:**

Following education on the study protocol, patients will be offered the option to enroll. Informed consent will be obtained by approved research personnel in a private area. If the patient agrees to participate, consent will be documented. Consent will occur the day of the scheduled ablation procedure.

### **Compensation for time and effort:**

There is no compensation for participation in this study as there are no additional expenses and time requirement beyond standard of care.

### **Risks/Benefits:**

The most common risks and discomforts expected in this study are rare but possible: development of a blood clot in the leg (less than 1%), bleeding (less than 1%) or a large bruise called a hematoma at the IV site (less than 1%).

Possible benefits, although unproven, may include less time in the post-procedure area and the ability to walk sooner after the ablation procedure. This study is designed to learn more about the use of percutaneous closure with the PerClose Proglide™ after atrial fibrillation ablation. The study results may be used to help others in the future.

#### **Data Analysis:**

The primary endpoint of the study will be time to hemostasis (starting from sheath pull) in minutes for the PC and MC groups. The secondary endpoints will include: 1) time to ambulation in minutes, 2) a composite of all major access site complications and venous thromboembolism, 3) each individual outcome comprising the composite outcome, 4) minor complications, 5) quality of life metrics (as measured by the inguinal pain questionnaire), 6) procedure length in minutes, 7) patient satisfaction, 8) pain medication requirement after hemostasis until discharge from the post-procedure area, 9) overall cost comparison related to hemostasis and complications over 30 days, 10) number of nursing encounters while in the post-procedure area. We will also compare all secondary endpoints between the primary and secondary treatment arms. Access related complications include: hematoma, hemorrhage, retroperitoneal bleeding, pseudoaneurysm, arteriovenous fistula, or access site infection.

Thromboembolism will include any arterial or venous thromboembolism that are clinically overt. Major complications will be defined as any of the above pre-specified complications that require direct procedural intervention (surgical or percutaneous repair), placement of an external compression hemostatic device (i.e. pneumatic compression dressing or femoral compression device), or medical therapy (including, but not limited to transfusion, reversal of anticoagulation, or initiation of other new medical therapy). Minor complications will include any complication that does not require any intervention beyond observation.

Normality of distribution of continuous variables will be tested using the Shapiro-Wilk test. Comparisons of continuous baseline variables across groups will be performed using Student's t and Mann-Whitney U tests for normally and non-normally distributed data, respectively. Comparison of categorical variables will be performed using Chi-squared and Fisher's Exact tests for binary categorical variables where appropriate, and Mann-Whitney U test for ranked ordinal level variables. Complication-free survival will be evaluated using Kaplan-Meier analysis, with separate strata for patients in each group. Patients will be censored at the time of their last confirmed encounter or at the completion of the follow up time of the study. All analyses will be performed using IBM SPSS ver. 25 (2017; IBM SPSS Statistics for Macintosh, Version 25.0. Armonk, NY: IBM Corp).

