## **Research Design:**

The study will occur in patients undergoing routine ablation for atrial fibrillation as standard of care. This is a prospective randomized trial. Patients will be randomized (see Randomization) in a 1:1 ratio to either manual compression or use of the PerClose for hemostasis at the end of the ablation procedure. Based on our clinical experience, we estimate the PerClose procedure for 3 access sites will require ~3 minutes of additional procedure time. In our experience, hemostasis is typically immediate (<1 minute to lock all three sutures) and this corroborated in the available literature. Prior published data for manual compression with figure-of-eight sutures are reported as 7.9 minutes. We also intend to have a secondary treatment arm in which post-hemostasis

ambulation time will be one hour (currently, the standard is two hours after vascular closure). The length of follow-up will be up to 30 days at routine clinical follow-up after the procedure.

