***Procedural data will include:***

- Time to hemostasis
- Case length (routinely collected)
- Anticoagulation time (ACT) at the completion of the case prior to sheath pull (routinely collected)
- Success rate of PerClose™ deployment and number of PerClose™ devices used.
- Success rate of hemostasis with manual compression or “figure-of-eight” suture.

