### **Randomization:**

Patients will be randomized in two one of two groups: those undergoing percutaneous closure with PerClose™ and those with manual compression (manual hemostasis with, or without “figure of eight” suture for hemostasis at the discretion of the treating physician). Patients will be randomized in a 1:1 ratio to groups and stratified on sex to ensure equal proportions of males and females in both groups. Block randomization with block sizes of 6 will be used. Blocks will be generated as needed using a computer model. In the PerClose arm, patients will be randomized secondarily in 1:1 fashion as either standard ambulation (2 hours bed rest) or early ambulation (1-hour bedrest) after hemostasis.

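### The primary endpoint has a start but no stop event common to both arms, so time to hemostasis may be measured to different events under PerClose and manual compression

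*Protocol*

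**What the plan says.** The Data Analysis section defines the primary endpoint in one sentence: "The primary endpoint of the study will be time to hemostasis (starting from sheath pull) in minutes for the PC and MC groups". The list of procedural data names the same variable without further definition.

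Research Design supplies the only operational detail. For PerClose, "hemostasis is typically immediate (<1 minute to lock all three sutures" is given as the investigators' experience. For the comparator, "Prior published data for manual compression with figure-of-eight sutures are reported as 7.9 minutes". The same section adds that "we estimate the PerClose procedure for 3 access sites will require ~3 minutes of additional procedure time", without saying whether those minutes lie inside the primary clock.

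The Randomization section leaves the control technique to the treating physician: "manual hemostasis with, or without “figure of eight” suture".

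The procedural data list records success in two different ways. For one arm it is "Success rate of PerClose™ deployment and number of PerClose™ devices used"; for the other it is "Success rate of hemostasis with manual compression or “figure-of-eight” suture".

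No section defines hemostasis as an observed state, says how or by whom it is confirmed, or says how several access sites combine into one time. None says what happens to the time when the assigned method fails or bleeding restarts. Later bleeding that needs a compression device counts as a major complication under Data Analysis, but its effect on the primary time is not stated.

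**The concern.** A duration needs two defined ends, and this one has only the first. Suture lock shows that a device step is complete. It does not by itself show that the site is dry. No comparable early step is given for manual compression, so staff could reasonably stop the PerClose clock at lock and the control clock once bleeding is seen to have stopped. Part of any difference would then come from the choice of stop event and not from the method of closure.

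Take a PerClose patient whose sutures lock at 1 minute, who then oozes and is compressed by hand for several minutes. Nothing in the protocol prevents that patient from being recorded as 1 minute and as a successful deployment, and nothing requires it.

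The stop time is recorded once, at the bedside. If different events were used, no later analysis plan could recover a common one, so the definition belongs in the protocol. The same undefined event also starts the randomized bed-rest periods (Randomization) and opens the window for pain medication (Data Analysis).

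**Working it through.** **1. The passages side by side**

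| Element | PerClose | Manual compression |
|---|---|---|
| Start of clock | Sheath pull | Sheath pull |
| Stop event in Data Analysis | None | None |
| Planning time in Research Design | Under 1 min, linked to suture lock | 7.9 min with figure-of-eight suture, end event not given |
| Success item | Deployment | Hemostasis |
| Effect of failure or re-bleeding on the time | Not stated | Not stated |
| Several sites: which sheath pull starts the clock | Not stated | Not stated |

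**2. The plan's own figure.** The protocol gives 50 per arm for 80% power at alpha 0.05, but no standard deviation, so this cannot be reproduced. Working backwards (normal approximation, two-sided), with a planning difference of 7.9 − 1 = 6.9 min:

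SD = 6.9 / [(1.960 + 0.842) × √(2/50)] = 6.9 / 0.560 = 12.3 min.

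This shows only what SD would be consistent with the plan. The point about the stop event does not depend on it.

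**3. Illustration of uncounted PerClose failures.** Inputs from the protocol: PerClose 1 min (an upper bound, since it says under 1 minute) and manual compression 7.9 min. Assumptions with no source in the protocol: a fraction f of PerClose patients need a further hold that is not counted, and that hold lasts 7.9 min (the comparator time, borrowed for scale).

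PerClose mean with the hold counted = 1 + f × 7.9; difference = 7.9 − that mean.

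| f | PerClose mean (min) | Difference (min) | Overstatement against 6.9 (min) |
|---|---|---|---|
| 0 | 1.0 | 6.9 | 0 |
| 5% | 1.4 | 6.5 | 0.4 |
| 10% | 1.8 | 6.1 | 0.8 |
| 20% | 2.6 | 5.3 | 1.6 |

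**4. The same omission in the control arm.** If a fraction g of manual-compression patients also had an uncounted 7.9-minute hold, the net overstatement would be 7.9 × (f − g). It is zero when f = g and reverses when g exceeds f. Missing failure rules alone therefore do not fix the direction; a stop event that differs by arm would.

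**5. The additional PerClose work.** If the roughly 3 minutes fall inside the clock and come on top of the 1 minute, the PerClose time is 1 + 3 = 4 min and the difference 7.9 − 4 = 3.9 min. If the locking minute is part of the 3, the difference is 7.9 − 3 = 4.9 min. If the 3 minutes fall outside, it stays at 6.9 min. On the protocol's own figures, this one unstated choice moves the planning difference by 2 to 3 minutes, more than the failure rates assumed in step 3.

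**The case against.** The strongest reply is that the endpoint is named once, for both arms, as time to hemostasis. In its ordinary meaning, a patient who is still oozing has not reached it, whatever the sutures are doing. The statement about suture lock is planning background, and the word typically allows hemostasis to come later than locking. The procedural data list keeps time to hemostasis separate from deployment success, and the success rates are not among the endpoints.

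Much of this stands. A reader might infer that the protocol stops the PerClose clock at suture lock, that failures never lengthen the time, that an unblinded operator makes both calls, or that manual compression can end only when pressure is lifted. The documents support none of these. They are silent on the end event in both arms and on who records it, and failed manual hemostasis is as unaddressed as failed PerClose closure. Nor is counting the manual hold a bias, since the length of the hold is part of the effect under study.

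The reply does not supply the missing criterion. Ordinary meaning does not say how dryness is confirmed, over how long, at which of several sites, or with what treatment of a failed method. The only operational detail on offer is specific to one arm.

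**Conclusion.** The point holds as a gap in the definition of the primary endpoint. There is no stop event common to both arms and no rule for failure, conversion or re-bleeding, and success is measured differently by arm. The arms may be timed to different events. Bias towards PerClose is possible if suture lock is used as its end, but the protocol does not establish that direction.

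The size cannot be computed from the protocol. The 6.5 to 5.3 minutes in the illustration rest on assumed failure rates of 5% to 20%, a borrowed 7.9-minute hold and no uncounted failures in the control arm. A reader might take these as true differences or conclude that the primary result would be overturned. Neither follows, since even the 20% case leaves 5.3 of 6.9 minutes. What is at risk is the interpretation of the size of the difference. The definition should be settled before times are recorded.

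**What to change.** In Data Analysis:

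- Stop the clock in both arms at the same observed state: all access sites without active bleeding and with no pressure applied, confirmed over the same short fixed observation period, wherever the sheaths are pulled.
- State that if the assigned method fails, or bleeding restarts within a window fixed identically for both arms, the time runs to final hemostasis and the patient stays in the assigned group.
- State whether the roughly 3 minutes of PerClose work fall inside the clock, and which sheath pull starts it when there are several sites.

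In the procedural data list, replace the two unlike success rates with one for both arms: hemostasis achieved with the assigned method alone.

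The bed-rest and pain-medication passages that refer to hemostasis should be reconciled with the adopted definition. These are changes to measurement only and need not alter how bleeding is managed.

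The cost is protocol wording, a brief identical check in both arms, and probably a slightly less favourable PerClose time.

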## **Introduction/Background:**

Radiofrequency ablation for treatment of atrial fibrillation (AF) using percutaneous venous access at the groin is one of the most common procedures performed by cardiac electrophysiologists. However, compared to other catheter-based interventions, patients undergoing AF ablation pose a unique set of challenges. First, AF ablation requires multiple points of transfemoral venous access with large diameter sheaths, ranging in size from 8F to 14F for cryoablation procedures. Second, operators are forced to balance the competing risk of thrombosis and bleeding in these patients. In order to minimize the risk of intraprocedural thrombosis, anticoagulation with heparin with a goal anticoagulation time (ACT) >300-350 seconds is necessary. However, operators typically require ACTs to normalize prior to removal of sheaths and manual compression, which significantly delays hemostasis and ambulation. While reversal agents are an option, there is currently clinical equipoise on their role and safety in this setting and they require additional time to exert their full effect. Lastly, patients require at least 1-2 months of therapeutic oral anticoagulation after the procedure to mitigate ongoing stroke risk. These factors culminate in longer times to hemostasis and ambulation and raise concerns for post-procedure access related complications for patients undergoing AF ablation. PerClose ProglideTM has recently gained FDA approval for closure of percutaneous venous access sites for catheter-based interventions and remains the only commercially available solution for access sites >14F inner diameter. Percutaneous closure of venotomy sites may facilitate rapid hemostasis without the need for reversal of anticoagulation, potentially attenuating bleeding risk. Additionally, typical bedrest times after percutaneous closure are based on data derived from arterial closure. Prior limited data, as well as frequent anecdotical reports, have suggested that earlier ambulation may be feasible. Because the venous circulation is a lower pressure system, it is possible that earlier than standard ambulation times after PerClose is both safe and feasible. However, a rigorous prospective investigation of the PerClose ProglideTM device in the context of AF ablation has not been performed.

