## **Objectives/Hypotheses:**

We hypothesize that, among patients undergoing ablation for AF, percutaneous closure of access sites with PerClose ProglideTM will lead to shorter times to hemostasis as compared to manual compression. Our secondary hypothesis is that patients undergoing PerClose after AF ablation, will be able to safely ambulate at one hour, as opposed to two hours, after hemostasis. We will also evaluate several other secondary endpoints comparing those undergoing PerClose to those undergoing manual hemostasis including: frequency of access site related complications, pain and need for post-procedure narcotics, patient satisfaction, as well as cost and overall resource utilization.

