***Post procedural data collected will include:***

- Time to ambulation after ablation
- Major and minor\* access related complications prior to discharge, at 48 hours, and at 30 day follow up appointment:
  - Superficial bruising
  - Hematoma
  - Retroperitoneal bleeding
  - Hemorrhage of any kind
  - Need for transfusion of blood products

- Pain (see below).
- Presence of post-procedure venous thromboembolism
- \*A major complication would be defined as the following: management, at the discretion of the treating physician, requiring direct procedural or medical intervention (other than observation) for any complication noted above.
- Groin access site pain as measured by:
  - A 10-point visual analog scale (0 = none; 10 = worst imaginable) on discharge, as validated in the PEVAR trial, and is already routinely used at our institution.
  - By short form inguinal pain questionnaire on 30-day follow up.
  - Opiate medication requirement prior to discharge (total dosage to be standardized to milligrams of morphine).
  - Opiate medication prescription on discharge (binary).
- Economic and cost data related to:
  - The cost of the PerClose devices used.
  - Ancillary resource utilization (i.e. devices used for hemostasis, sutures for “figure of eight”, cost of protamine for heparin reversal if used)
  - Length of stay
  - Post-procedure area time
  - Access site complication related cost including imaging required for workup and any interventions for management including medications administered or procedure charges.
- Nursing utilization (number of nursing encounters while in the post procedure area [routinely collected]).

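### Time to ambulation: pooling all PerClose patients against manual compression adds about 30 minutes that come from the bed-rest assignment, not the device

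*Protocol*

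**What the plan says.** The Randomization section forms two groups in a 1:1 ratio, PerClose and manual compression. It then adds a second randomization inside one of them only: "In the PerClose arm, patients will be randomized secondarily in 1:1 fashion as either standard ambulation (2 hours bed rest) or early ambulation". Early means one hour, and both rest periods run from hemostasis.

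The Data Analysis section gives time to hemostasis in the two groups as the primary endpoint and continues: "The secondary endpoints will include: 1) time to ambulation in minutes, 2) a composite of all major access site complications and venous thromboembolism". No subset of the PerClose arm is named for time to ambulation. The section then adds: "We will also compare all secondary endpoints between the primary and secondary treatment arms". Research Design uses the term secondary treatment arm for the one-hour group. The primary treatment arm is not defined anywhere.

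Other sections bear on the reading:

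- Objectives/Hypotheses mentions ambulation only within PerClose, where patients "will be able to safely ambulate at one hour, as opposed to two hours, after hemostasis".
- Introduction/Background makes delayed ambulation part of the case for the device. It says "operators typically require ACTs to normalize prior to removal of sheaths and manual compression, which significantly delays hemostasis and ambulation", and, of the challenges it lists, "These factors culminate in longer times to hemostasis and ambulation".
- The list of post-procedural data has "Time to ambulation after ablation", whereas bed rest is counted from hemostasis. Data Analysis gives no time origin for the endpoint.
- The only statement of a standard is in Research Design: "currently, the standard is two hours after vascular closure". No bed-rest time is given for manual compression.

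**The concern.** Time to ambulation is largely set by the bed rest a patient is assigned, and by design that assignment differs between the two groups. A shorter time in the PerClose arm would be read as a benefit of the device, because the Introduction presents the device as an answer to late ambulation. Part of the difference would be there even if the device did nothing, since half of one arm is told to get up an hour sooner.

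The added comparison of treatment arms would display the effect of the bed-rest order. It would not take that effect out of PerClose versus manual compression. If two-hour PerClose patients walked up to 30 minutes later than manual compression patients, the pooled mean would still show no loss, or a gain, for PerClose.

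The time origin blurs the contrast further. Counting from the end of ablation brings any wait for the ACT to normalize into the apparent device effect; counting from hemostasis does not.

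**Working it through.** The protocol gives no figure for this contrast, so there is none to reproduce.

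**Inputs from the protocol.** Assigned rest is 120 or 60 minutes, split 1:1, in PerClose only (Randomization). The enrolment goal is about 65 per arm (Full Study Cohort). Hemostasis takes under 1 minute with PerClose and 7.9 minutes with manual compression and figure-of-eight sutures (Research Design).

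**Assumptions, because the protocol is silent.** These are the standard deviation (SD) of time to ambulation, the bed rest after manual compression (M), and D, the true mean for manual compression minus that for two-hour PerClose. D includes hemostasis, any ACT wait and any difference in bed-rest rule.

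**Step 1: size of the shift.** Pooled PerClose mean rest = 0.5 × 60 + 0.5 × 120 = 90 minutes.

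- Pooled contrast minus two-hour contrast = (M − 90) − (M − 120) = 30 minutes for every M.
- With 32 of 65 patients on early ambulation: 60 × 32/65 = 29.5 minutes.
- If the early half actually walks only 45 or 30 minutes sooner: 0.5 × 45 = 22.5 or 0.5 × 30 = 15 minutes.

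**Step 2: an example with the protocol's own hemostasis times.** Assume M = 120, no ACT wait, and 1 minute for PerClose hemostasis.

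- Two-hour PerClose: (7.9 + 120) − (1 + 120) = 6.9 minutes.
- Pooled PerClose: (7.9 + 120) − (1 + 90) = 36.9 minutes.

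**Step 3: range over D.** The pooled contrast is D + 30, and the share due to the bed-rest order is 30/(30 + D).

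| Assumed D (min) | Pooled contrast (min) | Share from bed-rest order |
|---|---|---|
| −30 | 0 | – |
| 0 | 30 | 100% |
| 30 | 60 | 50% |
| 60 | 90 | 33% |
| 120 | 150 | 20% |

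**Step 4: how often the shift alone would be declared a difference.** Simulated normal data, 65 manual compression versus 33 + 32 PerClose, early mean 60 minutes lower, t-test at two-sided 5%.

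| Assumed SD (min) | D = 0, pooled: rejects | D = 0, two-hour PerClose only: rejects | D = −15, pooled: declares PerClose faster |
|---|---|---|---|
| 30 | >99% | 5% | 63% |
| 45 | 94% | 5% | 36% |
| 60 | 76% | 5% | 24% |
| 90 | 44% | 5% | 14% |

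At D = −15, manual compression versus two-hour PerClose declares PerClose faster in at most 0.3% of trials. At 50 per arm and D = 0, a Mann-Whitney test on the pooled arm rejects in 99% of trials at SD 30 and 62% at SD 60, so the result does not hinge on the t-test.

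**Step 5: precision of the alternative contrast.**

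- True standard error ratio = √[(1/65 + 1/32.5)/(2/65)] = 1.22.
- The reported standard error rises less, because the 60-minute gap between the halves adds 30² = 900 to the variance of the pooled arm. Pooled: √[(2·SD² + 900)/65]. Two-hour only: √[SD²(1/65 + 1/32.5)].
- At SD 30, 45, 60 and 90 these are 6.45, 8.73, 11.16, 16.22 and 6.45, 9.67, 12.89, 19.34; the ratios are 1.00, 1.11, 1.15, 1.19.
- A true D of 30 minutes would be detected by manual compression versus two-hour PerClose in >99%, 87%, 63% and 34% of trials.

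**The case against.** The strongest reply is that the pooled comparison is inferred. Data Analysis attaches the two group names to the primary endpoint only, and Objectives/Hypotheses frames ambulation solely as one hour versus two within PerClose, then lists other endpoints for PerClose versus manual compression. If the primary treatment arm means PerClose with standard ambulation, the plan may already intend the right contrasts. This stands as a real ambiguity. It does not clear the text, because the arm is undefined and the word *also* makes the arm comparison an addition to one already described.

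A second reply is that an SAP could settle which patients enter each contrast, and that the time origin and the bed rest after manual compression are missing detail. Those two points could be set aside. The main point remains, since the protocol itself creates the imbalance and lists the endpoint without restriction.

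Third, pooled PerClose versus manual compression is a valid randomized comparison, and the bed-rest effect would be reported beside it. That is true, but a 50/50 mix of two bed-rest orders is neither the standard nor the early strategy, and showing the order effect separately does not remove it.

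Fourth, the rejection rates rest on assumed SDs and D. That is fair. With an early mean of 60 minutes counted from hemostasis, normal data at SD 60 or 90 imply about 16% or 25% negative times, and the protocol's hemostasis times and ACT wait suggest a positive rather than a negative D. Those rates are illustrations; the 30 minutes does not depend on them.

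**Conclusion.** The concern holds on the plain reading of Data Analysis, and the wording should be fixed. Pooling adds 30 minutes (29.5 with a 33/32 split) in favour of PerClose to the time-to-ambulation contrast. This rests only on the 1:1 second randomization and on patients walking when their assigned rest ends; with partial adherence it shrinks, for example to 15 or 22.5 minutes. Its share of the observed difference is unknown, because D is not given.

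The claim is limited to one secondary endpoint. Time to hemostasis and procedure length are not affected. For complications, opiate use, nursing encounters and cost, the direction and size of any early-ambulation effect are unknown.

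**What to change.** In Data Analysis, state that for time to ambulation the device contrast is manual compression versus PerClose with two hours of bed rest, and that the bed-rest contrast is one-hour versus two-hour PerClose. Define primary and secondary treatment arm to match, and state the time origin of the endpoint.

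Reconcile Research Design, Randomization and Data Analysis on which bed-rest rule applies after manual compression; no rule is proposed here. If it differs from that of the two-hour PerClose group, describe the contrast as the device together with its bed-rest rule.

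For complications, opiate use, nursing encounters and cost, keep all PerClose versus manual compression and show the three groups beside it. Time to hemostasis and procedure length keep the full PerClose arm.

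The cost is wording only, with no added patients or data and no safety data dropped. The device contrast on this endpoint uses about half of the PerClose patients, so its true standard error is about 22% larger. At an assumed SD of 45 minutes, the reported 95% confidence interval half-width becomes about 19 instead of 17 minutes (1.96 × 9.67 versus 1.96 × 8.73).

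### The pain-medication endpoint has two stop points, and the one used for analysis is expected to differ in length between arms, most clearly between 1-hour and 2-hour bed rest

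*Protocol*

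**What the plan says.** Two sections of the protocol describe the same measure.

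- **Post-procedural data list:** "Opiate medication requirement prior to discharge", with the total expressed as milligrams of morphine. The place of discharge is not qualified. The same list has "Length of stay" and "Post-procedure area time" as separate items.
- **Data Analysis, secondary endpoint 8:** "pain medication requirement after hemostasis until discharge from the post-procedure area".

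Three other statements bear on how long the second window lasts and how the endpoint is used.

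- **Randomization:** PerClose patients are randomized again, 1:1, to "either standard ambulation (2 hours bed rest) or early ambulation (1-hour bedrest) after hemostasis".
- **Risks/Benefits:** possible but unproven benefits "may include less time in the post-procedure area and the ability to walk sooner after the ablation procedure".
- **Data Analysis:** every secondary endpoint is also to be compared between the primary and secondary treatment arms, so endpoint 8 is compared between groups with different assigned bed rest.

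The Objectives section names pain and the need for narcotics after the procedure together, as one item in the PerClose versus manual comparison.

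**The concern.** There are two linked problems.

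First, one endpoint has two end times. The protocol itself treats time in the post-procedure area and length of stay as different quantities, so discharge and leaving that area cannot be assumed to be the same moment. The same doses could give two different totals, and the protocol does not say which is the endpoint.

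Second, the endpoint is a cumulative dose over a window whose length is itself a possible result of the assignment. The window starts at hemostasis, which is also where the randomized bed rest starts. It ends when the patient leaves an area that the trial hopes patients will leave sooner. If it is shorter in one arm, that arm has less time in which doses can be counted. Because the Objectives put narcotic need beside pain, a lower total is likely to be read as less pain when part of it may be less time observed.

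**Working it through.** The protocol gives no figure for pain-medication use or for length of stay in the area, so there is no stated number to reproduce. The check is a comparison of text followed by an illustration.

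**Step 1. The two definitions side by side**

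| Element | Post-procedural data list | Data Analysis, endpoint 8 |
|---|---|---|
| Drugs | Opiates, in morphine milligrams | Pain medication, no unit |
| Start | Not stated; the list heading places it after the procedure | After hemostasis |
| Stop | Discharge, not qualified | Leaving the post-procedure area |

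The stop points differ in substance. The drug wording is tighter in one place than in the other. The start is imprecise in the list.

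**Step 2. Does the endpoint 8 window depend on assignment?**

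- Start of window: hemostasis.
- Start of assigned bed rest: hemostasis.
- Assigned bed rest within the PerClose arm: 1 hour or 2 hours.
- End of window: leaving the area, where a shorter stay is a possible benefit.

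A difference in window length between the two bed-rest groups is therefore to be expected, but it is not stated as a fact. No section ties leaving the area to the end of bed rest.

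**Step 3. Illustration of size, 1-hour versus 2-hour bed rest**

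Assumptions, none of them in the protocol:

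- the rate of opiate use per hour is constant and equal in both groups;
- the stay in the area equals assigned bed rest plus a further x hours, with the same x in both groups.

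Expected dose is then proportional to window length:

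ratio (1-hour / 2-hour) = (1 + x) / (2 + x); apparent reduction = 1 − ratio.

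| x (hours) | Ratio | Apparent reduction |
|---|---|---|
| 0 | 1/2 = 0.50 | 50% |
| 0.5 | 1.5/2.5 = 0.60 | 40% |
| 1 | 2/3 = 0.667 | 33% |
| 2 | 3/4 = 0.75 | 25% |
| 4 | 5/6 = 0.833 | 17% |

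If leaving the area is not tied to bed rest, the two windows have the same expected length and the reduction is 0%. If doses cluster soon after hemostasis, so that the rate is not constant, the effect is smaller than in the table.

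**Step 4. PerClose versus manual compression**

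The protocol assigns no bed-rest time to the manual compression group, so the same calculation cannot be made for the main comparison.

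**The case against.** Several points can fairly be made on the other side.

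- **Collection and analysis are different things.** Doses may be collected to discharge and analysed to an earlier time without conflict, provided they are timed, and exact windows are often left to the SAP, which is not shown. This narrows the first problem. It does not remove it, because the protocol already fixes two stop points and does not say how they relate.
- **The start and the drug class.** A reader might infer that opiates given during the ablation would be counted, or that endpoint 8 brings in every analgesic. The documents do not support either reading. The item stands under a post-procedural heading, apart from the procedural list; the Objectives speak of narcotics after the procedure; and no non-opiate analgesic is collected. What remains is loose wording, including whether the list starts at the end of the procedure or at hemostasis.
- **Bias toward PerClose.** A reader might also infer that the endpoint favors PerClose over manual compression. The protocol does not show this. The window opens after hemostasis, so faster hemostasis does not itself shorten it, and there is no bed-rest time for the manual group to compare with.
- **The total is a legitimate outcome.** Medication needed until the patient leaves recovery is a reasonable measure of resource use under a strategy, and pain is measured directly by a visual analog scale at discharge and a questionnaire at 30 days. This stands. It is a reason to keep a total, but not to read that total as pain without allowing for time observed.

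**Conclusion.** The point holds in a limited form. The two sections give different stop points, and tighter versus looser drug wording, for one secondary endpoint. They must be reconciled. The window in the Data Analysis section is expected to differ by assignment, most clearly between the two bed-rest groups, so a lower cumulative dose there could partly reflect shorter observation.

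It would go too far to say that assignment does shorten the window: the shorter stay is described only as possible and unproven. The size is unknown. The range of 0% to 50% is an illustration that rests on the assumed link to bed rest, the assumed further stay and the constant rate of use. It is not an estimate.

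This concerns one of ten secondary endpoints. It is a worthwhile clarification, not a threat to the trial's main conclusion.

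**What to change.** Use one definition in the post-procedural data list and in the Data Analysis section:

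- opiate dose in morphine milligrams, counted from hemostasis;
- analysed over a window of pre-specified length, the same for all arms and set before any outcome data are seen, or as dose per hour observed;
- with the total to discharge reported beside it as a resource measure.

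Doses within the fixed window should count wherever in the hospital they are given, so that leaving the post-procedure area no longer ends observation. The window should not be set from the shortest stay seen in the trial, since that depends on the data and could discard much of the relevant use.

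**Cost.** The change is one of wording, plus extraction of dose administration times from records. A short fixed window omits later doses. Dose per hour avoids that, but if use is concentrated soon after hemostasis it would make the arm with the shorter stay look worse; the fixed window is free of this. The total to discharge may itself vary with assignment through length of stay, so it should not replace the common window.
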